20.2.1.3 Follow-up Visits

- **At 6 (± 1) weeks from screening (transitioning subjects) or baseline (BAX 855 naïve subjects)**
- **Subsequently: Every 3 months (± 2 weeks) starting from screening (transitioning subjects) or baseline (BAX 855 naïve subjects)**

From this timepoint, procedures for subjects on the fixed dose prophylactic regimen are identical, apart from confirmation of eligibility for transitioning subjects at the 6 ± 1 weeks visit (which was done at ED1 for BAX 855 naïve subjects).

At least 84 to preferably 96 hours must have elapsed since the previous BAX 855 administration and the subject must not be actively bleeding.

The following assessments will be performed:

Pre-infusion:

- Confirmation of eligibility for transitioning subjects (at the 6 ± 1 weeks visit)
- Physical examination, including height (for subjects aged < 18 years at enrollment) and body weight
- Review and discuss subject e-diary, including:
 - Review bleeding episodes and their treatment
 - Adverse events
 - Concomitant medications and non-drug therapies
- Laboratory assessments within 30 minutes of start of infusion
 - FVIII activity and antigen

- TGA parameters (optional)
- VWF antigen (optional)
- Immunogenicity tests
- Hematology, clinical chemistry and lipid panel
- Vital signs (within 15 minutes of IP infusion)

Determination of IR

- Infusion of 60 ± 5 IU/kg BAX 855

Post-infusion:

At 30 ± 15 min post-infusion:

- FVIII activity and antigen
- TGA parameters (optional)
- Vital signs

Other procedures:

- Dispense IP:
 - A sufficient quantity of IP will be dispensed to cover the period until the next scheduled visit.

Intermittent procedures, every 6 months:

- Every 6 months PROs will be assessed:
 - Bleed and pain severity using Haemo-SYM (≥ 18 years), HRQoL using SF-36 (≥ 14 years), HRQoL using PedsQL (< 14 years), patient satisfaction with treatment using the Satisfaction Questionnaire (all ages), and Patient Activity Level (all ages).
- In subjects who are HIV positive, CD4 counts should be tested every 6 months.

20.2.1.4 End of Study Visit

The procedures listed here should also be performed if a subject withdraws or discontinues from the study. At least 84 to preferably 96 hours must have elapsed since the previous BAX 855 administration and the subject must not be actively bleeding.

The following assessments will be performed:

Pre-infusion:

- Physical examination, including height (for subjects aged < 18 years at enrollment) and body weight
- Pregnancy test if female of childbearing potential
- Collection of subject e-diary and review of entries and discussion with subject
 - Review bleeding episodes and their treatment
 - Adverse events
 - Concomitant medications and non-drug therapies
- PROs:
 - Bleed and pain severity using Haemo-SYM (≥ 18 years), HRQoL using SF-36 (≥ 14 years), HRQoL using PedsQL (< 14 years), patient satisfaction with treatment using the Satisfaction Questionnaire (all ages), and Patient Activity Level (all ages)
- Laboratory assessments within 30 minutes of start of infusion:
 - FVIII activity and antigen
 - TGA parameters (optional)

- VWF antigen(optional)
- Immunogenicity tests
- Hematology, clinical chemistry and lipid panel
- Vital signs (within 15 minutes of IP infusion)

Determination of IR

- Infusion of 60 ± 5 IU/kg BAX 855

Post-infusion:

At 30 ± 15 min post-infusion:

- FVIII activity and antigen
- TGA parameters (optional)
- Vital signs

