Subjects receiving a PK-tailored prophylactic treatment regimen will have their PK assessment performed following eligibility confirmation. Following PK assessment, they undergo their baseline visit and subsequent visits every 3 months following their baseline visit for IR determination, efficacy and safety assessment and e-diary review. In addition, at 4, 8 and 18 weeks after the baseline visit, subjects' FVIII levels, TGA parameters and VWF antigen will be measured to ensure that FVIII trough levels of $\geq 3\%$ are maintained, and, if necessary, dose adjustments will have to be performed. Also, hemostatic efficacy and clinical safety will be assessed and e-diary reviewed.

Investigators will review e-diaries for untoward events, concomitant medications, non-drug therapies, and patient reported outcomes (PROs; see Section 10.5.2). Safety assessments performed at the study visit will include immunogenicity (inhibitory antibodies for FVIII and binding antibodies for FVIII, BAX 855, PEG, and CHO), and changes in conditions of the physical examination, vital signs, and clinical laboratory assessments (hematology, clinical chemistry, and lipids). Subjects who develop a high responder inhibitor (> 5 Bethesda Units [BU]), or who develop a low responder inhibitor (≤ 5 BU but ≥ 0.6 BU) that cannot be adequately managed by the prescribed prophylaxis regimen with BAX 855 will be discontinued from study. At every study visitⁱⁱⁱ, IR for FVIII activity and TGA parameters (optional in subjects receiving fixed dose prophylaxis) will be determined within 30 minutes prior to infusion with 60 ± 5 IU/kg BAX 855 and 30 ± 15 minutes following the infusion. Also, TGA parameters and pre-infusion VWF antigen level will be assessed in subjects receiving a PK-tailored dosing (optional for subjects aged < 12 years).

The sponsor will suspend enrollment and treatment if 2 or more subjects develop anaphylaxis after BAX 855 treatment. The sponsor may stop this study at any time. In addition, the sponsor may modify the study based on results of the other BAX 855 studies.

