8.3 Duration of Study Period(s) and Subject Participation

The overall duration of this continuation study is estimated to be approximately 4 years from study initiation (ie, first subject enrolled by signing informed consent) to study

ⁱⁱⁱ Except at visits 4 ± 1 , 8 ± 1 and 18 ± 2 weeks following baseline in those subjects receiving PK-tailored treatment regimen.

completion (ie, last subject last visit). Recruitment of transitioning subjects will continue until the last subject has completed any other BAX 855 study.

Each subject will participate in the study until a total of at least 100 EDs to BAX 855 has been achieved (accumulated across all BAX 855 studies in which each subject participated). Depending on the subject's BAX 855 exposure history and treatment regimen given, the planned duration of subject participation to reach the 100 EDs (from enrollment to subject completion) can vary from approximately 3 to 12 months. However, extension of the study duration for individual subjects beyond the 100 EDs may be granted.

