9.3 Withdrawal and Discontinuation

Any subject may voluntarily withdraw (ie, reduce the degree of participation in the study) consent for continued participation and data collection. The reason for withdrawal will be recorded on the End of Study eCRF. Assessments to be performed at the end of study visit (including in cases of withdrawal or discontinuation) are described in Section 10.6 and Section 20.3.

Discontinuation (ie, complete withdrawal from study participation) may be due to dropout (ie, active discontinuation by subject) or loss to follow-up (ie, discontinuation by subject without notice or action). Additionally, the investigator and sponsor have the discretion to discontinue any subject from the study if, in their judgment, continued participation would pose an unacceptable risk for the subject.

Subjects also may be withdrawn from treatment or discontinued from further study participation for the following reasons:

- The subject develops a confirmed high responder inhibitory antibody to FVIII (>5 BU by Nijmegen modification of the Bethesda assay) or a low responder inhibitory antibody (≤ 5 BU but ≥ 0.6 BU) that cannot be managed by the protocol-required treatment.
- The subject experiences a severe anaphylactic reaction to BAX 855.
- The subject requires therapy with another PEGylated product (eg, PEG-Interferon).
- The subject frequently misses administration of IP (ie, misses more than 30% of planned prophylactic doses within any 3-month period).
- The subject is non-compliant with study procedures, in the opinion of the investigator.

- The subject repeatedly uses another FVIII therapy for prophylaxis (in the absence of an acceptable justification to the sponsor) or for the treatment of bleeding episodes.
- The subject requires a surgical or dental procedure and is not eligible or does not consent for the surgery study, or participates in the surgery study and then refuses to resume participation in this continuation study. If the surgery study is closed, the subject will be withdrawn from the continuation study.
- The subject experiences a life-threatening bleeding episode (eg, any gastrointestinal hemorrhage or intracranial hemorrhage).
- The subject experiences severe trauma or requires emergency surgery with FVIII replacement therapy other than BAX 855.

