20.2.2.6 End of Study Visit

The procedures listed here should also be performed if a subject withdraws or discontinues from the study. At least 84 to preferably 96 hours must have elapsed since the previous BAX 855 administration and the subject must not be actively bleeding.

The following assessments will be performed:

Pre-infusion:

- Physical examination, including height (for subjects aged < 18 years at enrollment) and body weight
- Collection of subject e-diary and review of entries and discussion with subject
 - Review bleeding episodes and their treatment
 - Adverse events
 - Concomitant medications and non-drug therapies
- PROs:
 - Bleed and pain severity using Haemo-SYM (≥ 18 years), HRQoL using SF-36 (≥ 14 years), HRQoL using PedsQL (< 14 years), patient satisfaction with treatment using the Satisfaction Questionnaire (all ages), and Patient Activity Level (all ages)
- Laboratory assessments within 30 minutes of start of infusion:
 - FVIII activity and antigen assays
 - TGA parameters and VWF antigen (optional in subjects aged < 12 years)
 - Immunogenicity tests
 - Hematology, clinical chemistry and lipid panel
- Vital signs (within 15 minutes of IP infusion)

Determination of IR:

- Infusion of 60 ± 5 IU/kg BAX 855

Post-infusion:

At 30 ± 15 min post-infusion:

- FVIII activity and antigen
- TGA parameters (optional in subjects aged < 12 years)
- Vital signs

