20.3 Schedule of Study Procedures and Assessments

20.3.1 Subjects Transitioning from Other BAX 855 Studies on Fixed Dose Prophylactic Treatment Regimen

Procedures/Assessments	Screening Visit ^a	Follow-Up Visits		End of Study Visit ^b
		6 ± 1 Weeks Following Screening	Every 3 Months ± 2 Weeks Following Screening	
Informed consent ^c	X			
Eligibility criteria	X			
Confirmation of eligibility		X		
Medical history	*			
Medication history	*			
Concomitant medications ^d	*	X	X	X
Non-drug therapies ^d	*	X	X	X
Physical exam	*	X	X	X
Adverse events ^d	*	X	X	X
Laboratories ^e	*	X	X	X
Vital signs ^f	*	X	X	X
Bleeding episodes and their treatment ^d	*	X	X	X
Pregnancy test ^g	X			X
PROs ^h	X		X ⁱ	X
Patient e-diary ^j	X	X	X	X
IR determination ^k	X	X	X	X
Dispense IP	X ^k	X	X	

^a The screening visit coincides with the end of study visit of the previous BAX 855 study. The procedures/assessments marked with an asterisk (*) will be transcribed from the end of study visit of the previous BAX 855 study. The following assessments are not part of the end of study assessments of the previous BAX 855 study and must be performed at screening to ensure eligibility: Performance score (Karnofsky or Lansky), viral serology (see Section 20.4.1), and pregnancy test if female of childbearing potential. Additionally, for subjects transitioning from the surgery study (Study 261204), FVIII assays and lipid panel (see Section 20.4.1) should also be performed.

^b Including cases of withdrawal or discontinuation.

Continued on Next Page

Continued

- ^c Occurs at enrollment at latest (prior to any study-specific procedure); to give the patient sufficient time to review the ICF, this document should preferably be provided prior to the end of study visit of the previous study.
- ^d Indicates that concomitant medications, non-drug therapies, adverse events, and bleeding episodes and their treatment will be continuously reviewed and specifically assessed at these times by the study sites and discussed with the subject.
- ^e For laboratory assessments, see Section 20.4.1.
- ^f Vital signs to include body temperature (°C), respiratory rate (breaths/min), pulse rate (beats/min), and systolic and diastolic blood pressure (mmHg).
- ^g A hCG urine pregnancy test will be done on all females of childbearing potential at the screening and end of study visit.

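### The end-of-study lists apply the 60 ± 5 IU/kg BAX 855 recovery infusion to every withdrawn subject, with no exemption for severe anaphylaxis or pregnancy

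*Protocol*

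**What the plan says.** **Visit lists.** Protocol 20.2.1.4 (fixed dose) and 20.2.2.6 (PK-tailored) open with the same sentence: "The procedures listed here should also be performed if a subject withdraws or discontinues from the study". The stated conditions for the visit are washout ("At least 84 to preferably 96 hours must have elapsed since the previous BAX 855 administration") and no active bleeding. Each list then orders the 60 ± 5 IU/kg IR infusion, followed at 30 ± 15 minutes by FVIII activity and antigen, TGA and vital signs.

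**Tables.** The End of Study column marks IR determination in 20.3.1 to 20.3.3 and post-infusion FVIII in 20.4.1 to 20.4.3. Its footnote in each table reads "Including cases of withdrawal or discontinuation".

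**Design section.** Section 8.2 says that at every study visit IR "will be determined within 30 minutes prior to infusion with 60 ± 5 IU/kg BAX 855". Footnote iii gives the only exception: "Except at visits 4 ± 1 , 8 ± 1 and 18 ± 2 weeks following baseline in those subjects receiving PK-tailored treatment regimen".

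**Withdrawal.** Section 9.3 says "Subjects also may be withdrawn from treatment or discontinued from further study participation for the following reasons", and one listed reason is "The subject experiences a severe anaphylactic reaction to BAX 855". For pregnancy the same list is firm: product exposure stops. For the assessments due on withdrawal, Section 9.3 sends the reader to Sections 10.6 and 20.3. Section 10.6 asks sites to make every effort to complete the termination visit.

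**The concern.** A site that withdraws a subject for severe anaphylaxis and follows the protocol's own references goes from 9.3 to 10.6 and then to 20.3 and 20.4. The visit it finds there includes a full dose of the product that caused the reaction, and nothing at that point tells it to leave the dose out. The consequence, if it happened, could be life-threatening.

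The protocol treats hypersensitivity as a real risk. Section 6.5 notes anaphylaxis reported with ADVATE, which shares the core protein, and possible reactions through anti-PEG antibodies. Section 9.2.2 excludes naïve subjects with known hypersensitivity to PEG. The study-level rule in 8.6 needs two or more anaphylaxis cases, so it does not protect the first one, and Section 16.4 provides no data monitoring committee.

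Pregnancy raises a plainer conflict, because one section stops the product and another schedules it.

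**Working it through.** The plan states no figure to reproduce. The check is a comparison of sections, plus one subtraction.

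**1. Where the infusion is applied to withdrawn subjects**

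| Place | Infusion at End of Study | Covers withdrawal | Exemption by reason |
|---|---|---|---|
| 20.2.1.4, 20.2.2.6 | ordered | yes | none |
| 20.3.1, 20.3.2, 20.3.3 | IR determination marked | yes, by footnote | none |
| 20.4.1, 20.4.2, 20.4.3 | post-infusion FVIII marked | yes, by footnote | none |
| 8.2 | every study visit | not addressed | none (footnote iii concerns visit timing) |

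The count is 2 lists, 3 + 3 = 6 tables and 1 design section, with 0 exemptions by reason. The footnote in 20.4.1 that makes IR conditional on confirmed eligibility is attached to the follow-up columns, not to End of Study.

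**2. Pregnancy**

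The 20.2.1.4 list has a pregnancy test before the infusion but does not say what to do if it is positive. The 20.2.2.6 list has no pregnancy test, although table 20.3.3 schedules one at End of Study.

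**3. Provisions that could stop the infusion**

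- 9.3: a subject may be withdrawn from treatment, and the investigator or sponsor may discontinue a subject at unacceptable risk. The anaphylaxis wording is permissive; the pregnancy wording is not.
- 12.2 and 15.5: the investigator may act against an immediate hazard without prior sponsor approval.
- 8.6 and 8.2: treatment is suspended or stopped at two or more anaphylaxis cases, and the sponsor may stop the study on its own safety assessment.
- 12.1.1.1 and 2: a severe hypersensitivity reaction to BAX 855 is a named SAE, reportable within 24 hours of awareness.

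None of these is repeated or cross-referenced in the two visit lists or the six tables.

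**4. Notice to the sponsor**

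Inputs: minimum washout 84 h (20.2.1.4 and 20.2.2.6); reporting limit 24 h (Section 2).

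Minimum notice = 84 − 24 = 60 h, counted from the infusion that caused the reaction and assuming the site learns of the reaction at once. If the site learns t hours later, the minimum is 60 − t. The washout is itself a minimum, so there is no upper bound.

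**5. What depends on the infusion**

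Only end-of-study IR and the post-infusion FVIII activity and antigen, TGA and vital signs. The physical examination, PROs, immunogenicity tests, hematology, chemistry, lipids and pre-infusion samples do not need it. The inhibitor test behind the primary safety outcome is therefore unaffected.

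**6. Probability**

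Re-exposure needs a severe anaphylactic reaction and then a decision to infuse despite it. The documents give no rate for the first beyond phase 1, which had no allergic reactions in 19 treated subjects after single doses. They give nothing for the second. No estimate is offered.

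**The case against.** The strongest answer is that Section 9.3 already covers the case. A subject withdrawn from BAX 855 treatment for severe anaphylaxis is naturally read as receiving no more BAX 855, and that specific provision should prevail over a general visit list worded with should. Sections 12.2 and 15.5 also let the investigator withhold the dose. Section 10.6 foresees contact between investigator and sponsor when an adverse event leads to discontinuation. Re-exposure would require a clinician to give the product knowingly, the subject to agree, and a sponsor already told of the SAE not to intervene.

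Most of this stands, and it is why the point is minor. It does not close the gap, for three reasons. The infusion is listed as a visit procedure for IR, so a site could take it to lie outside treatment. Sections 12.2 and 15.5 are routes for urgent measures and deviations, with immediate notice to the sponsor and written confirmation within 1 calendar day; a foreseeable contraindication should not need them. And the pregnancy rule in 9.3 is in direct conflict with the visit list, which no reading of may or should removes.

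A reader might infer that the protocol forces re-challenge after anaphylaxis, or leaves such a subject unprotected. The documents do not support either reading, because the provisions above allow the dose to be withheld.

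**Conclusion.** Minor; a cheap patient-safety improvement. The End of Study instructions apply the IR infusion to all withdrawn or discontinued subjects without exemption. Taken literally, they re-expose a subject withdrawn for severe anaphylaxis and contradict Section 9.3 in pregnancy. Confidence is high for this textual gap, and it does not extend to any expected harm.

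Actual re-exposure is unlikely, given the power to withhold and the sponsor's notice of at least 60 hours, which assumes same-day awareness at the site. Pregnancy should also be rare in an X-linked recessive disorder (Section 6.2). A reader might want to turn an assumed anaphylaxis rate into a probability of harm, but that would measure anaphylaxis, not re-infusion after it.

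No sample size or error rate depends on this point.

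**What to change.** Add the following to both lists (20.2.1.4 and 20.2.2.6), as a footnote to the End of Study columns in 20.3 and 20.4, and as an exception in 8.2:

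*The IR infusion and all post-infusion assessments are omitted when the subject is withdrawn for severe anaphylaxis/hypersensitivity to BAX 855 or pregnancy (including a positive test at this visit), when treatment has been stopped under 8.6, or when the investigator judges further BAX 855 contraindicated (eg, a high-responder inhibitor); all pre-infusion assessments are still performed.*

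Also add the pregnancy test to the pre-infusion list in 20.2.2.6, so that the list agrees with table 20.3.3 and the new sentence refers to a procedure the list contains.

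The drafting cost is one sentence in two lists, one footnote in six tables, one exception in 8.2 and one added list item. The data cost is the loss, in a few withdrawn subjects, of end-of-study IR and post-infusion FVIII activity and antigen, TGA (not optional for PK-tailored subjects aged 12 or over) and vital signs. SAP Section 6.7 ends the efficacy observation period at the last BAX 855 infusion. If the IR infusion counts there, omitting it ends the period at least 84 hours earlier and removes one exposure day in those same few subjects.

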20.2.2 Subjects on PK-Tailored Prophylactic Treatment Regimen

20.2.2.1 Screening Visit

Subjects who decide to **switch** to a PK-tailored treatment regimen at any time during the continuation study will start with the procedures from the PK assessment visit (if one is needed), but the screening visit is not applicable.

The screening procedures differ according to whether the subject is **transitioning from a previous BAX 855 study** (see Section 20.2.1.1.1) or is **BAX 855 naïve** (see Section 20.2.1.1.2).

20.2.2.1.1 Subjects transitioning from other BAX 855 studies

The screening visit coincides with the end of study visit of the previous BAX 855 study.

Informed consent must be obtained at enrollment at the latest (prior to any study-specific procedure); to give the patient sufficient time to review the ICF, this document should preferably be provided prior to the end of study visit of the previous study.

At least 84 to preferably 96 hours must have elapsed since the previous BAX 855 administration and the subject must not be actively bleeding.

The relevant data obtained at the end of study visit of the previous study will be transcribed to the screening visit eCRF of this continuation study, and where possible, duplication of blood draws or evaluations will be avoided.

The following procedures will be performed:

- Ensure informed consent has been obtained
- Assess performance score (Karnofsky [\geq 16 years] or Lansky [$<$ 16 years])
- Laboratory assessments:
 - Viral serology:
 - HIV: HIV-1 and HIV-2 Ab (PCR to be performed if positive)
 - HBV: HBsAg, HBsAb, HBcAb
 - HCV: HCVAb (PCR to be performed if positive)
 - CD4 count, if subject is HIV positive
- Pregnancy test if female of childbearing potential
- Assessment of inclusion/exclusion criteria
- Provide a subject e-diary and give instructions on use.

The following data will be obtained/transcribed from the end of study visit of the previous BAX 855 study:

- Medical History
- Medication history
- Concomitant medications
- Non-drug therapies
- Physical examination
- Vital signs
- Adverse events
- Laboratory data^{xx}:

^{xx} Note: For subjects transitioning from the surgery study (Study 261204), FVIII activity and FVIII antigen and lipid panel should also be performed.

- FVIII assays: FVIII activity (activated partial thromboplastin-based 1-stage clotting assay and chromogenic assay) and FVIII antigen (pre- and post-infusion values, if IR assessed in previous study's end of study visit)
- Immunogenicity tests: Inhibitory antibodies to FVIII (Nijmegen assay), binding antibodies (IgG and IgM) to FVIII, BAX 855, and PEG, anti-CHO antibodies
- Hematology, clinical chemistry, and lipid panel

BAX855 Infusion:

- Administration of first prophylactic infusion of BAX 855 using a fixed dose prophylactic treatment regimen as used in the previous study.

OR

- If IR is to be assessed (BAX855 pivotal: optional; BAX855 surgery: not applicable): Administration of 60 ± 5 IU/kg of BAX855
 - At 30 ± 15 min post-infusion:
 - FVIII: FVIII activity (1-stage clotting assay and chromogenic assay) and FVIII antigen
 - Vital signs (body temperature, respiratory rate, pulse rate, and supine systolic and diastolic blood pressure)

Transitioning subjects who **have undergone a PK assessment** in a previous BAX 855 study do not need to undergo a PK assessment in this study, but can start their PK-tailored prophylactic treatment at the next visit (Baseline visit) at 6 ± 1 weeks after the screening visit. A sufficient quantity of IP will be dispensed to continue with their previous prophylactic BAX 855 treatment regimen until the Baseline visit. Subjects who received on-demand treatment in the pivotal study (Study 261201) will first receive a fixed dose prophylactic treatment regimen (as outlined in section 8.7.3.1) until their dose and frequency is determined and the first PK-tailored dose administered.

→ See Section “Baseline visit / Start of prophylaxis” (see Section 20.2.2.3) for further procedures

Those who **have not undergone a PK assessment** in a previous BAX 855 study must attend a PK assessment visit. A sufficient quantity of IP will be dispensed to continue with their previous BAX 855 treatment regimen until the PK assessment within 45 days from screening.

→ See Section “PK assessment for BAX 855 naïve subjects and transitioning subjects with no prior PK assessment” (see Section 20.2.2.2) for further procedures

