8.7.3 Description of Treatment

Subjects will be treated on either a fixed dose or PK-tailored prophylactic treatment regimen^{iv} until they reach at least 100 EDs (accumulated across all studies). Subjects who received on-demand treatment in the pivotal study (Study 261201) and decide to receive a PK-tailored treatment regimen in this study will first receive a fixed dose prophylactic treatment regimen (as outlined in Section 8.7.3.1) until their dose and frequency is determined and the first PK-tailored dose administered.

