10.3.1 Subjects Transitioning from Other BAX 855 Studies

Subjects transitioning from other BAX 855 studies can use the end of study assessments in their previous BAX 855 study for screening visit assessments in this continuation study. Any additional required screening assessments will be performed the same day. Subjects will return to the study site no later than 6 (\pm 1) weeks after the end of study visit in their prior study/continuation study's screening visit to confirm eligibility.

Additionally, transitioning subjects will receive IP treatment either as part of the IR determination of the end of study visit of the previous BAX855 study or the first IP treatment will be given at the screening visit of this continuation study to subjects transitioning from other BAX 855 studies.

Transitioning subjects^x who decide to receive a PK-tailored treatment regimen will continue receiving their study-specific treatment regimen with BAX 855^{xi} (eg, twice weekly 45 ± 5 IU/kg) until baseline/start of PK-tailored prophylaxis. The study-specific prophylactic treatment regimen will be interrupted by one infusion for PK determination in those subjects for whom PK is not yet available.

x As well as subjects who are already participating in the continuation study.

xi NOTE: This refers to the type of treatment that subjects will receive with BAX 855 from this continuation study (not from the previous BAX 855 study).

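### The interim regimen before PK-tailored dosing is stated inconsistently, and for former on-demand subjects without a prior PK assessment Protocol 20.2.2.1.1 can be read as continuing on-demand treatment until the PK visit

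*Protocol*

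**What the plan says.** Three parts of the protocol describe treatment between entry and the first PK-tailored dose for subjects who come from another BAX 855 study.

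- **Section 8.7.3** sets a rule for "Subjects who received on-demand treatment in the pivotal study (Study 261201"). If they choose tailoring, the rule reads "and decide to receive a PK-tailored treatment regimen in this study will first receive a fixed dose prophylactic treatment regimen", and it lasts until the first tailored dose. Prior PK is not a condition.
- **Section 10.3.1** has transitioning subjects who choose tailoring stay on their study-specific regimen "until baseline/start of PK-tailored prophylaxis". Footnote xi explains that this means the treatment "subjects will receive with BAX 855 from this continuation study (not from the previous BAX 855 study"). The next sentence describes subjects whose PK is not yet available as interrupting a prophylactic regimen for one PK infusion.
- **Section 20.2.2.1.1** (PK-tailored, transitioning subjects) offers at screening either an IR infusion or a first prophylactic infusion "using a fixed dose prophylactic treatment regimen as used in the previous study". It then splits by PK history. Subjects with a prior PK continue their previous prophylactic regimen to the Baseline visit, and a sentence there repeats the on-demand exception of 8.7.3. For subjects without a prior PK, product is "dispensed to continue with their previous BAX 855 treatment regimen until the PK assessment within 45 days from screening", and no exception follows.

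Section 20.2.2.2 then dispenses product to transitioning subjects for the 6 ± 1 weeks from PK assessment to Baseline and names no regimen.

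**The concern.** The sections disagree on whose regimen applies in the interim: this study's (10.3.1) or the previous study's (20.2.2.1.1). For a subject who was already on twice-weekly prophylaxis the two may amount to the same thing. For a former on-demand subject they do not. Because 20.2.2.1.1 states the on-demand exception in one paragraph and omits it from the next, a site could conclude that it does not apply in the second.

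Two sites could then treat the same kind of subject differently while each follows the protocol. At stake are whether scheduled prophylaxis is given in this interval, the exposure-day count (the study's target is at least 100 per subject), and the regimen to which the interval and any bleeds in it are assigned.

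**Working it through.** The plan gives no figure to reproduce. The check sets the texts side by side and then bounds the interval and the number of subjects.

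**1. The rule for a former on-demand subject who chooses tailoring**

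| Protocol section | Prior PK? | Interim regimen | Until |
|---|---|---|---|
| 8.7.3 | not a condition | fixed-dose prophylaxis | first tailored dose |
| 10.3.1 and footnote xi | either | this study's regimen, not the previous study's | baseline |
| 20.2.2.1.1 | yes | previous prophylactic regimen, but on-demand subjects go to fixed dose | Baseline visit; for the exception, first tailored dose |
| 20.2.2.1.1 | no | previous regimen, no exception | PK assessment, within 45 days of screening |
| 20.2.2.2 | no | not named | Baseline, 6 ± 1 weeks later |

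The fourth row conflicts with the first two. The previous regimen of a former on-demand subject was on-demand treatment.

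**2. Does the screening infusion settle it?** No. It refers to a fixed-dose prophylactic regimen used in the previous study, and a former on-demand subject had none there. The alternative at that visit is a single IR infusion, which starts no regimen.

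**3. Length of the conflict.** The conflicting text ends at the PK assessment, so the limit is 45 days from screening. Section 8.7.3.1 gives the fixed regimen twice weekly, on average one infusion per 3.5 days:

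45 / 3.5 = 12.9, or about 13 scheduled prophylactic infusions given or not, depending on the section followed.

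**4. Number of subjects.** Section 6.1 plans 17 on-demand subjects and a PK group of 25 in the pivotal study. It does not say how many of the 25 were on demand. Because 25 exceeds 17, all or none of the 17 could have prior PK. The numbers who transition and who choose tailoring at entry are also not given. Subjects who switch to tailoring later skip this screening visit (20.2.2.1). The range is therefore 0 to 17. Against the planned enrolment of about 250, the upper end is 17 / 250 = 6.8%.

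**5. Route to the spontaneous ABR.** SAP 6.7 starts the efficacy period on the PK-guided regimen at the first prophylactic infusion and computes observation time per regimen. SAP 7.1 derives the ABR per regimen, and SAP 5.11 takes the regimen from the assignment and change-of-assignment forms. There are two cases at screening:

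- If a fixed-dose prophylactic regimen really starts, there is no on-demand time.
- If an IR infusion is given instead, the PK-guided period has not begun.

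On-demand time would enter the PK-guided rate only if an infusion labelled prophylactic were given at screening, on-demand treatment followed, and the interval were assigned to the PK-guided regimen. The SAP has no category for on-demand time within this study, so misassignment cannot be ruled out. Nothing in the documents shows that it would happen.

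**The case against.** The strongest reply is that no section says any subject stays on demand. Section 8.7.3 is the treatment section and its rule is unconditional. Section 10.3.1 describes subjects awaiting PK as being on a prophylactic regimen. The study offers only fixed-dose or PK-tailored prophylaxis, apart from the every-5-day and every-7-day regimens retained under footnote iv. The prophylactic infusion at screening comes before the split by PK history. On this view 20.2.2.1.1 is an incomplete paragraph in a supplement and not a second rule.

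Much of this stands. The on-demand reading rests on the literal meaning of the previous regimen and on a missing exception. The reply does not remove the conflict, however. Section 10.3 sends sites to Supplement 20.2 for the required procedures, no rule of precedence between the sections was found, and an exception repeated in one of two parallel paragraphs suggests that it is absent from the other by intent.

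It is also fair that the wider difference between previous-study and this-study wording has little shown consequence for subjects already on prophylaxis. Section 6.1 says the fixed regimens here are aligned with those of the pivotal and pediatric studies. The demonstrated difference concerns former on-demand subjects only.

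A reader might make two stronger inferences:

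- **That the on-demand interval runs on to Baseline**, adding the 6 ± 1 weeks after the PK assessment. The text does not support this. The conflicting wording stops at the PK assessment, and 20.2.2.2 is silent on the regimen, so 8.7.3 and 10.3.1 apply there.
- **That on-demand bleeds inflate the co-primary ABR by a stated amount.** The documents give no bleed rates for these subjects from which to calculate one, and the per-regimen derivation in the SAP means the interval does not automatically enter the PK-tailored rate.

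**Conclusion.** The inconsistency is real and lies in current protocol text. It leaves the interim treatment of a small, uncounted group, at most the 17 planned, open to two readings for no more than 45 days each. The infusion count assumes twice-weekly dosing over the full interval, so it is an upper figure. The range of subjects rests on the pivotal study's planned and not actual numbers.

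Exposure-day counts would differ between the two readings. Bias in the spontaneous ABR remains a possibility only. The point deserves correction because it is a conflict between stated treatment instructions, not because a distorted primary result has been shown.

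**What to change.** Reconcile Protocol 8.7.3, 10.3.1 (with footnote xi), 20.2.2.1.1 and 20.2.2.2 so that:

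- one interim regimen is stated for transitioning subjects who choose PK-tailored dosing;
- the former on-demand case is covered explicitly in both paragraphs of 20.2.2.1.1, with and without prior PK;
- the screening-infusion text in 20.2.2.1.1 no longer points to a previous-study regimen that some subjects did not have;
- 20.2.2.2 names the regimen for the weeks between PK assessment and Baseline.

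Which regimen applies is for the sponsor and clinical team to decide. SAP 6.7 needs a line excluding on-demand time and bleeds from the prophylaxis observation period only if the reconciled protocol leaves any on-demand interval. The cost is a short clarifying amendment, with no extra data or visits.
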